7 STATISTICAL METHODS & DETERMINATION OF SAMPLE SIZE

7.1 Statistical and Analytical Plans

For the primary endpoint, the focus will be the point estimate, and determination of sample size is based on practical consideration rather than power calculation. It is planned to randomize a total of 90 subjects, 30 subjects per arm.

For the point estimate, with 30 subjects per arm, the precision of the estimates of the primary endpoint is provided by the following 95% confidence intervals (Table 6):

Table 6. Primary Endpoint Precision of Estimates

Sample Size	Number of Subjects Meeting the Primary Endpoint	Point Estimate (%)	95% Confidence Interval
30	8	26.7	(10.8, 42.5)
30	10	33.3	(16.5, 50.2)
30	12	40	(22.5, 57.5)
30	14	46.7	(28.8, 64.5)

Complete and specific details of the statistical analysis will be described and fully documented in the Statistical Analysis Plan (SAP). The SAP will be finalized prior to the interim database lock. The statistical analyses will be performed using SAS (SAS Institute Inc., Cary, North Carolina, USA).

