APPENDIX E. SUBJECTS CONTINUING PARTICIPATION

This appendix outlines the modifications to the study procedures and depatuxizumab mafodotin dosing in subjects who are currently receiving depatuxizumab mafodotin and who choose to continue depatuxizumab mafodotin treatment after the results from the pre-planned interim efficacy analysis for Study M13-813 (INTELLANCE-1).

As a result of the interim efficacy analysis for INTELLANCE-1 study, AbbVie determined it was appropriate to allow subjects who are receiving depatuxizumab mafodotin to continue doing so based on investigator and subject decision.

Subjects who decide to continue treatment with depatuxizumab mafodotin must voluntarily sign and date the updated informed consent form, approved by an Independent Ethics Committee (IEC)/Institutional Review Board (IRB).

Study Activities

Only study activities necessary for study drug dosing, safety monitoring and adverse event reporting will be continued. The revised schedule of study assessments for these subjects is provided in the table below.

Study Activities	28-Day Cycles ^a					Final Study Drug Visit ^d /At Progression	35-Day F/U ^e	49-Day F/U
	Day 1 of Every Cycle (1, 2, 3 etc.)	Day 1 of Odd-Numbered Cycles (1, 3, 5, etc.)	Day 1 of Cycle 2	Day 15 of Every Cycle ^b	Day 22 of Every Cycle ^c			
Symptom-directed Physical Exam	X ^f			X ^f				
Ophthalmology Exams		X ^g				X ^g	X ^g	
Chemistry	X					X	X	
Hematology	X				X	X	X	
Adverse Event Assessment and Concomitant Medications	X			X		X	X	X ^k
Temozolomide Administration	X ^h							
Depatuzumab Mafodotin Administration	X ⁱ			X ⁱ				
Treatments for OSE	X ⁱ			X ⁱ				

F/U = Follow-up; OSE = ocular side effect

- Assessments will be based on 28-day treatment cycles, with the first cycle starting approximately 4 weeks after completion of radiation therapy. Subjects will receive concomitant TMZ and depatuzumab mafodotin for the first 6 cycles, and study drug monotherapy for an additional 6 cycles or until disease progression or study drug discontinuation.
- Day 15 visit will not be performed after discontinuation of depatuzumab mafodotin treatment.

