- As per TMZ prescribing information, during the 28-day cycle of TMZ, a blood count for ANC and platelets should be performed 21 days (\pm 2 days) after the start of each TMZ cycle. If the ANC falls below 1,500/ μ L or if the platelet count falls below 100,000/ mm^3 , then blood counts should be performed weekly until recovery to these levels before TMZ dosing. A certified local lab may be used instead of central lab; if so, ANC and platelet results should be reported in the eCRF. Day 22 testing may be omitted for cycles in which TMZ is not administered or if local prescribing information allows for a different testing schedule for ANC and platelets.
- Final Study Drug Visit to be performed approximately 14 days after last dose of depatuzumab mafodotin.
- To be performed 35 days (\pm 3 days) after the last dose of depatuzumab mafodotin. If the Final Study Drug Visit is more than 35 days after the last dose of study drug, then 35-day safety follow-up procedures will not be performed.
- Physical exams will be performed only as needed for safety management and AE/SAE reporting.
- Ophthalmology exams will be performed only as needed for safety management and AE/SAE reporting. The last ophthalmology exam following discontinuation of depatuzumab mafodotin may be done at the 35-Day F/U or 49-Day F/U Visit. Targeted ophthalmology exam data will not be collected by the Sponsor.
- TMZ will be administered once daily on Days 1 through 5 of each 28-day cycle for 6 cycles per the local prescribing information.

- i. Depatuxizumab mafodotin infusion will be administered on Day 1 and Day 15 of each 28-day cycle for 12 cycles.
- j. Patient will receive management of ocular side effects as per investigator discretion. In this case, depatuxizumab mafodotin dose interruption and/or reduction may be used, and any available prophylactic or supportive care measures may be employed without restriction, at the discretion of the investigator. Refer to Section 5.7 of the protocol.
- k. If the subject is unable to return to the site for the Day 49 Follow-Up Visit, a phone call may be conducted to obtain AE/SAE and concomitant medication information.

Depatuxizumab Mafodotin Administration and Individual Subject Discontinuation

Depatuxizumab mafodotin will be administered as described in the protocol.

Subjects may continue receiving depatuxizumab mafodotin while drug supply is available, as long as disease progression has not been determined.

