5.3 Endpoints

5.3.1 Primary Endpoint

The primary endpoint is defined as the percentage of subjects with either a ≥ 3 -line decline from baseline ($\geq +0.3$ on LogMAR scale) (Bailey IL, Lovie-Kitchin, 2013) in

visual acuity (with baseline correction determined at the screening ophthalmology visit) or \geq Grade 3 OSE severity on the Corneal Epithelial Adverse Event (CEAE) scale, either of which will indicate inadequate control of OSEs requiring a change in OSE management strategy. The primary endpoint is assessed over 8 weeks after initiation of depatuxizumab mafodotin treatment regardless of phases.

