6.0 Analysis Populations

All the analyses will be carried out on the safety population. The **safety population** will comprise all randomized subjects who have received at least 1 dose of Depatux-M. Subjects will be classified according to prophylactic treatment received. The safety population will be the primary analysis population for analysis of all endpoints.

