11.2 Analysis of Primary Endpoint

The proportion of patients who met the primary endpoint defined as (a) either $\geq +0.3$ change on LogMAR scale in baseline adjusted visual acuity or (b) incidence of \geq Grade 3 Corneal Epithelial Adverse Event (CEAE, CMQ: 80000184), anytime over 8 weeks after initiation of Depatux-M and prior to BCL intervention will be summarized by treatment arms and in overall population. This analysis will also be repeated for the Post-BCL intervention period. For the Post-BCL intervention period, analysis will be

limited to the patients who received BCL intervention and baseline will be re-set to the last assessment prior to start of BCL intervention.

Time to the first occurrence (onset) of any CEAE will be assessed using Kaplan Meier methodology and median time to first onset of any corneal AE (along with 95% CI). This analysis will be repeated for Grade 3 or higher corneal AEs.

Time to onset will be measured in days relative to the date of first dose date to the start date of the first occurrence of CEAE. If a subject has not experienced an CEAE, the subject will be censored on the subject's last assessment date (i.e., the day of the subject's last known laboratory assessment, last known vital sign assessment, last known physical exam, last known ocular exam, last known tumor assessment, or last known follow-up visit, whichever is the latest) or 49 days from the subject's last treatment (Depatux-M), whichever is earliest. If the subject has no post-baseline assessment, the data will be censored on the day of first dosing date.

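### The primary 8-week percentage has no rule for subjects whose pre-BCL observation is incomplete, so any such subjects count by default as non-events and pull the arm percentages down

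*SAP*

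**What the plan says.** **Population.** SAP 6.0 defines the safety population as "all randomized subjects who have received at least 1 dose of Depatux-M" and adds: "The safety population will be the primary analysis population for analysis of all endpoints". It sets no minimum follow-up and no evaluability condition.

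**Endpoint.** SAP 5.3.1 fixes the window: "The primary endpoint is assessed over 8 weeks after initiation of depatuxizumab mafodotin treatment regardless of phases". SAP 11.2 then reports a simple proportion, with events counted "anytime over 8 weeks after initiation of Depatux-M and prior to BCL intervention will be summarized by treatment arms and in overall population". It mentions no confidence interval for this proportion, although Protocol 7.4 planned 95% intervals by arm.

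**Censoring elsewhere.** SAP 11.2 has a censoring rule for time to first CEAE. SAP 11.3 plans a time-to-event analysis of the same composite before BCL and censors event-free subjects at the last assessment. It does not ask for an estimate at 8 weeks, gives no time origin for the composite, and is not linked to the primary percentage.

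**Early stop.** Enrolment ended at 40 subjects (Protocol 2.2, SAP 4.0). Those who continue treatment move to Protocol Appendix E, which according to Protocol 2.2 collects only AE and SAE safety data. Its schedule has no CEAE row and no chemoradiation visits, and a footnote states: "Targeted ophthalmology exam data will not be collected by the Sponsor".

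**The concern.** A crude proportion estimates the 8-week risk only if 8-week status is known for everyone in the denominator. A dosed subject who leaves observation at week 4 without an event is counted exactly like one examined through week 8 without an event. An event that goes unobserved can only be missing from the numerator, so the effect on the percentage is zero or downward, never upward.

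This matters because the primary objective is to estimate that percentage in each arm, and the SAP is descriptive, with no test beside it. The SAP was written for the stopped trial, and stopping is what makes incomplete observation more likely. An understated percentage would make each prophylactic regimen look better than it is.

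**Working it through.** **1. The plan's own figure.** Protocol 7.1 states: "It is planned to randomize a total of 90 subjects, 30 subjects per arm". Table 6 follows from the Wald interval p ± 1.96·√(p(1 − p)/n). For 12/30: 0.40 ± 1.96·√(0.24/30) = 0.40 ± 0.175, that is 22.5% to 57.5%, as printed. The rows for 8, 10 and 14 events also reproduce. The planned precision therefore treats the 8-week status of all 30 subjects per arm as known.

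**2. Where observation could end before 8 weeks.**
- Loss to follow-up or withdrawal of consent.
- A CEAE grade recorded as not evaluable (Operations Manual 3.15 and Appendix H). SAP 11.2 has no rule for this.
- A subject still in chemoradiation when data collection was cut back. Appendix E gives no visits for that phase. Operations Manual 4.3 keeps CEAE entries off the standard AE forms, except ulceration or perforation, so both components of the composite could be lost.
- A symptom-free subject who stops after the first infusion. The last fixed visit is 49 days after the last dose: Day 1 + 49 = Day 50, while 8 weeks ends at Day 1 + 56 = Day 57. After a second infusion on Day 15 the visit falls on Day 64 and the gap closes.

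**3. Size of the effect.** Inputs, all assumed because the documents give no count: p = true 8-week risk; d = share of subjects cut short; s = share of the risk already elapsed at cut-off.

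Expected crude percentage = p·[1 − d(1 − s)]

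| d | p = 40%, s = 1/2 | p = 40%, s = 0 |
|---|---|---|
| 5% | 39.0% | 38.0% |
| 10% | 38.0% | 36.0% |
| 20% | 36.0% | 32.0% |
| 30% | 34.0% | 28.0% |

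For example, 0.40·[1 − 0.10·0.5] = 0.38. With d = 20%, a true risk of 26.7% (lowest row of Table 6) becomes 24.0% (s = 1/2) or 21.4% (s = 0). A true risk of 61% becomes 54.9% or 48.8%; that is the INTELLANCE-1 rate of Grade 3 or higher corneal events, which is not limited to 8 weeks and serves only as an upper end.

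**4. A rough idea of d.** Assume uniform enrolment of 40 subjects up to the amendment date of 28 May 2019. Starting from protocol version 1.0 (18 December 2017, 526 days), the number inside a 56-day window on that date is 40·56/526 = 4.3. Starting from version 2.0 (2 July 2018, 330 days) it is 40·56/330 = 6.8. That is 11% to 17% of subjects. If enrolment ended earlier, or sites implemented the amendment later, it is fewer, possibly none.

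**5. What an estimate that allows for censoring would show.** Take an arm of 13 (40/3 = 13.3) with 5 observed events and m subjects cut short event-free. The crude percentage is 5/13 = 38.5% whatever m is. The single-interval actuarial estimate is 5/(13 − m/2):

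| m | Crude | Actuarial | If all m had events |
|---|---|---|---|
| 0 | 38.5% | 38.5% | 38.5% |
| 1 | 38.5% | 40.0% | 46.2% |
| 2 | 38.5% | 41.7% | 53.8% |
| 4 | 38.5% | 45.5% | 69.2% |

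**6. Against sampling error.** The Wald interval for 5/13 is 12.0% to 64.9%, about 26 points either side. A shift of 2 to 4 points is small beside that, but it always points the same way.

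**The case against.** The case against has several good parts.

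- **No truncated subject is documented.** The SAP's remark that most subjects lacked long-term follow-up does not concern an 8-week window. This stands, and the size of the effect is unknown.
- **Appendix E mostly starts too late to matter.** Its cycles are described "with the first cycle starting approximately 4 weeks after completion of radiation therapy". With about 6 weeks of radiation that is about week 10, after the window has closed. Protocol 8.1 requires ethics approval before an amendment is implemented, and Appendix E requires a new consent, so the switch was not immediate. This stands for on-schedule subjects. What remains is those still in chemoradiation at the switch, for whom Appendix E gives no schedule.
- **Stopping Depatux-M does not end observation.** Protocol 4.1 and 5.6 keep such subjects under ocular follow-up. This stands. A reader might infer that a subject who received one or two infusions does not belong in the denominator. The documents do not support that: the objective is the percentage needing a change in OSE management, and a subject who stops early, is still assessed and needs no change is a valid non-event.
- **SAP 11.3 already censors.** True, but it produces no 8-week figure that can be set beside the primary percentage.
- **Kaplan-Meier has its own faults.** Censoring deaths overstates incidence, and withdrawal in glioblastoma may be informative. The first is met by treating death as a competing event; the second remains a limitation.
- **Arm differences.** A reader might infer a spurious gap of about 8 points between identical arms: 40% against 0.40·[1 − (4/13)·(2/3)] = 31.8%. That needs 4 subjects cut short in one arm and none in the other. If 4 of 40 were cut short at random, with arms of 13, 13 and 14, all four fall in one arm with probability (715 + 715 + 1,001)/91,390 = 2.7%.

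**Conclusion.** The gap is real: the primary percentage covers every dosed subject, has no rule for incomplete 8-week observation, and by default counts such subjects as non-events. To the extent that they exist, the arm percentages are biased low. With a true risk of 40% and half of it elapsed at cut-off, the expected loss is 2 points if 10% are cut short and 4 points if 20% are. These rates are assumptions, and the true number may be zero.

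Three stronger readings go beyond the documents. They do not show that the percentages are in fact biased low, because no count is given. The SAP does not declare truncated subjects adequately controlled; that result follows from its silence. And nothing here justifies displacing the protocol-defined percentage as the primary result. This is a cheap improvement to the analysis, not a demonstrated error in the result.

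**What to change.** In SAP 11.2, keep the crude percentage and add the following beside it, by arm and overall:

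1. The 8-week cumulative incidence of the same composite, from first Depatux-M dose, with 95% CI and death before an event as a competing event.
2. Censoring of event-free subjects at the last assessment that informs the composite, that is CEAE or visual acuity. The last-assessment date defined in SAP 11.2 for CEAE onset also admits laboratory, vital-sign and tumour assessments, which would extend event-free time without information on the eye.
3. The number observed event-free for the full 8 weeks and the number cut short. Completeness can be defined by a CEAE assessment in the Week 9 Day 1 window of SAP Table 1 (X = 5: Rx Days 14·5 − 19 = 51 to 14·5 − 6 = 64). Week 9 is a telephone CEAE assessment, so acuity completeness should be shown separately, up to the Week 7 examination.
4. One stated rule for BCL started without a qualifying event. SAP 11.3 counts it as an event; the 11.2 percentage by default does not.
5. A sentence saying that the crude percentage is interpreted in light of the cumulative incidence and these counts.

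The cost is some SAP wording and one extra table, from data already needed for SAP 11.3. The added estimate may be slightly wider and less favourable, and it assumes that censoring is unrelated to ocular risk. If nobody was cut short, the table shows that and the two estimates agree.

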The INTELLANCE-1 interim efficacy analysis results overall indicated no survival benefit for adding depatuxizumab mafodotin to standard RT/TMZ therapy in newly diagnosed GBM patients. However, given that no new clinically significant safety risks were identified, the RTOG Steering Committee and AbbVie believed it was appropriate to allow subjects receiving depatuxizumab mafodotin to continue depatuxizumab mafodotin treatment if the investigator and subject believed it is in the subject's best interest.

A total of 40 subjects have been enrolled in Study M16-534 (UNITE). Based on the results from INTELLANCE-1, no new subjects will be enrolled into Study M16-534 (UNITE). Subjects who are currently receiving depatuxizumab mafodotin will be allowed to continue depatuxizumab mafodotin treatment if the investigator and subject believe it is in the subject's best interest. **For those subjects who choose to continue depatuxizumab mafodotin, study procedures have been modified as described in Appendix E.** The appendix provides guidance for study drug administration and collection of only safety data related to AEs and SAEs. No additional efficacy data will be collected.

With all these changes, no statistical testing will be performed for the efficacy endpoints. Given only a small number of patients are enrolled in the study and most of them did not have long-term follow-up, all the efficacy endpoints will only be summarized, and no statistical model will be used to analyze the efficacy data. The statistical section remains unchanged to reflect the original analysis plan. An abbreviated SAP will be written to document the details about the analysis plan.

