7.2 Definition for Analysis Populations

The intent-to-treat (ITT) population will comprise all randomized subjects regardless of whether they receive study treatment (depatuxizumab mafodotin) or steroid-related OSE treatment. Since the

primary endpoint is a safety endpoint, the ITT will be used only for summary of enrollment and randomization.

The safety population will comprise all randomized subjects who have received at least 1 dose of depatuxizumab mafodotin. Subjects will be classified according to steroid-related treatment received. The safety population will be the primary analysis population for analysis of all endpoints including efficacy and safety endpoints.

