7.4 Statistical Analyses for Safety

For the primary endpoint of the study, the percentage of subjects with either a ≥ 3 -line decline from baseline ($\geq + 0.3$ on LogMAR scale) in visual acuity (with baseline correction) or \geq Grade 3 OSE severity on the Corneal Epithelial Adverse Event [CEAE] scale will be calculated for each arm and associated 95% confidence intervals will be provided. Comparisons between arms will be made using Chi-square test.

For secondary safety endpoints, continuous variables will be summarized with N, mean, standard deviation (SD), median, minimum, and maximum. Frequencies and percentages will be computed for the category variables. For time to event variables, Kaplan-Meier survival curves with median time and associated 95% confidence interval will be provided.

Detailed statistical analysis methods for primary and secondary safety endpoints will be provided in the statistical analysis plan (SAP).

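### The SAP gives the primary percentage in each arm no 95% confidence interval, although the protocol promises one, and it does not say what became of the protocol's chi-square comparison

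*SAP*

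**What the plan says.** **Protocol.** Section 7.1 says of the primary endpoint that "the focus will be the point estimate, and determination of sample size is based on practical consideration rather than power calculation". It then states "It is planned to randomize a total of 90 subjects, 30 subjects per arm", and Table 6 shows the 95% interval that 30 subjects would give at four possible event counts. Section 7.4 has the primary percentage calculated for each arm and adds that "associated 95% confidence intervals will be provided". Its next sentence reads "Comparisons between arms will be made using Chi-square test". It does not say whether that means three pairwise tests or one three-arm test, and it gives no significance level.

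**Amendment text.** After the INTELLANCE-1 result, Section 2.2 says that "no statistical testing will be performed for the efficacy endpoints". It adds that the statistical section is left as it was, to record the original plan, and that an abbreviated SAP will give the details. Section 7.3 names the efficacy endpoints as OS and PFS. Section 7.2 says that the "primary endpoint is a safety endpoint".

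**SAP.** Section 4.0 repeats that tests are dropped for efficacy endpoints and gives total enrolment as 40. Section 5.1 keeps the estimation objective. Section 11.1 has categorical safety endpoints summarised by frequencies and percentages. Section 11.2 says that the proportion meeting the primary endpoint "anytime over 8 weeks after initiation of Depatux-M and prior to BCL intervention will be summarized by treatment arms and in overall population". The only 95% interval named in 11.2 is for the Kaplan-Meier median time to onset of a corneal epithelial adverse event (CEAE).

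**The concern.** Estimation is the study's only stated primary aim, and interval width is the only description of precision that the protocol gives. The SAP is the operative analysis document, and it omits that interval for the primary estimate without saying so.

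Enrolment stopped at 40 of the planned 90, so precision is well below what Table 6 shows. Three bare percentages from about 13 subjects each are easily read as a ranking of the regimens. Nothing in the planned output would show the reader how little they separate the arms.

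The second gap is one of record. The protocol names a comparison for the primary endpoint, the withdrawal of testing does not by its words reach that endpoint, and the SAP is silent. A programmer or report author cannot tell whether the interval and the test were dropped on purpose.

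**Working it through.** **1. Reproduce Table 6.** Inputs from protocol 7.1: n = 30 and x = 8, 10, 12, 14. The Wald interval is p ± 1.96·√(p(1−p)/n).

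| x/30 | p (%) | Wald 95% CI, recomputed | Table 6 |
|---|---|---|---|
| 8 | 26.7 | 10.84 to 42.49 | 10.8 to 42.5 |
| 10 | 33.3 | 16.46 to 50.20 | 16.5 to 50.2 |
| 12 | 40.0 | 22.47 to 57.53 | 22.5 to 57.5 |
| 14 | 46.7 | 28.81 to 64.52 | 28.8 to 64.5 |

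All four rows match. Clopper-Pearson (8/30: 12.3 to 45.9) and Wilson (8/30: 14.2 to 44.4) do not, so Table 6 uses the Wald method.

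**2. Size per arm after the stop.** 40/3 = 13.3. An even split would be 13/13/14. This is an assumption: per-arm counts are not given, and SAP 6.0 classifies subjects by prophylactic treatment received.

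**3. Intervals at n = 13.** The Clopper-Pearson lower limit is the 0.025 quantile of Beta(x, n−x+1), and the upper limit is the 0.975 quantile of Beta(x+1, n−x).

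| x/13 | % | Clopper-Pearson 95% CI | Wilson 95% CI |
|---|---|---|---|
| 3 | 23.1 | 5.0 to 53.8 | 8.2 to 50.3 |
| 4 | 30.8 | 9.1 to 61.4 | 12.7 to 57.6 |
| 5 | 38.5 | 13.9 to 68.4 | 17.7 to 64.5 |
| 6 | 46.2 | 19.2 to 74.9 | 23.2 to 70.9 |
| 8 | 61.5 | 31.6 to 86.1 | 35.5 to 82.3 |

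**4. Width against Table 6.** At 5/13 the exact interval spans 68.4 − 13.9 = 54.5 points. The nearest Table 6 row (12/30) spans 57.5 − 22.5 = 35.0, a ratio of 54.5/35.0 = 1.56. Like for like, the exact interval at 12/30 is 22.7 to 59.4, a span of 36.7, and 54.5/36.7 = 1.49. Sample size alone gives √(30/13) = 1.52. So the intervals are about 1.5 times as wide.

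**5. Why the method must be named.** At n = 13 the Wald interval is −6.8% to 22.2% for 1/13 and 77.8% to 106.8% for 12/13. It has zero width at 0/13 and 13/13. Carrying the Table 6 method over would risk impossible limits.

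**6. Does the withdrawal of testing cover the primary endpoint?** Protocol 2.2 and SAP 4.0 limit it to efficacy endpoints. Protocol 7.3 gives OS and PFS as those endpoints, and 7.2 calls the primary a safety endpoint. The SAP agrees: Section 10.0 analyses no efficacy endpoint, while the primary is analysed under Section 11.0, Safety Analysis. By its words, then, the withdrawal does not reach the primary. An interval around one percentage is in any case neither a test nor a model.

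**7. Optional contrast, for scale.** For 4/13 against 6/13 the difference is 30.8 − 46.2 = −15.4 points. Newcombe's method uses the Wilson limits above:
- lower limit: −15.4 − √((30.8−12.7)² + (70.9−46.2)²) ≈ −46 points
- upper limit: −15.4 + √((57.6−30.8)² + (46.2−23.2)²) ≈ +20 points

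**The case against.** The strongest reply is that protocol 2.2 keeps Section 7 only as a record of the original plan and hands the analysis to the SAP. On that reading 7.4 is no longer live, and the SAP, which lists no test, governs. The trial was exploratory, unpowered and stopped early, so a descriptive summary is proportionate. This stands in part. It means the chi-square comparison should be called unresolved in the documents rather than still in force. It does not justify the missing interval, because the estimation objective is unchanged in SAP 5.1. It could also be said that a summary does not exclude an interval. That is true, but the 11.1 default points to percentages alone, and 11.2 names an interval where it wants one.

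A reader might infer more: that the chi-square test is unsuitable at this size and rejects too often. The documents do not support that. Exact enumeration of the Pearson test at a nominal 5%, over the Table 6 event rates, gives a size of 5.2% to 7.5% for 13 against 13. It gives only 4.6% to 5.3% for 13 against 14, and 5.0% to 5.2% for one three-arm test at 13/13/14. The excess therefore depends on an assumed exact split and on pairwise testing, which protocol 7.4 does not specify. Expected event counts at n = 13 fall below 5 at rates of 26.7% and 33.3% (3.5 and 4.3) but not at 40% or 46.7% (5.2 and 6.1).

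A reader might also infer that a between-arm contrast was promised and dropped. Neither document promises an interval for a difference. Its absence is not a broken commitment.

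**Conclusion.** The point holds for the per-arm interval. The protocol commits to a 95% interval for each arm's primary percentage, the SAP does not carry it over, and no stated withdrawal covers it. The omission matters because precision has fallen: at about 13 per arm an observed 38.5% is compatible with anything from 13.9% to 68.4%, about 1.5 times the width shown in Table 6.

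The status of the chi-square comparison is a smaller gap, closed by one explicit sentence. Leaving the test out is consistent with an estimation objective, and no claim is made here that the test would be invalid.

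The textual finding needs no assumption. The figures assume about 13 per arm from 40 enrolled and an even split, and the event counts are illustrations.

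**What to change.** In SAP 11.2, add two statements:

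1. The percentage meeting the primary endpoint will be reported for each arm with a two-sided 95% confidence interval. Name the method, Clopper-Pearson or Wilson, and do not use the Wald method behind Table 6.
2. The chi-square comparison in protocol 7.4 will not be performed for the primary endpoint.

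As an optional descriptive addition, report the risk differences B−A and C−A with Newcombe 95% intervals and no p-values.

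The cost is two sentences and extra columns in a table that is already planned, with no new data. The intervals will be visibly wide, which is what the reader needs to see.
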